- Able to complete a survey on a computer
- Able to complete surveys delivered via email
- Able to complete 3, 20 minute surveys during the study
- Able to complete surveys in the morning for 15 days

Exclusion Criteria:

- Currently using pharmacotherapy, a quitline, or a quit smoking program or support group for smoking cessation
- Participated in a research study about smoking cigarettes or using other tobacco products in the last 3 months

Recruitment

Recruitment data will be provided based on the CONSORT guidelines. The following CONSORT chart will be used as a template for reporting recruitment.

Withdrawal/follow-up

Level of withdrawal

- Data collection and the intervention occur using the same surveys, when a participant withdraws from data collection, they are withdrawing from follow up and the intervention.

Timing of withdrawal/lost to follow-up data

- Timing of withdrawal will be presented by treatment group, and categorized into each of the following timepoints:
 - o After baseline but before beginning intervention (before completing first daily survey)
 - o During intervention (days 1-15)
 - o During post-test follow up period (days 16-32)
 - o After post-test follow up period (after day 32)

Reasons and details of how withdrawal/lost to follow-up data will be presented

- Numbers (with reasons) of loss to follow up and withdrawal over the course of the trial will be summarized by treatment group

Baseline participant characteristics

List of baseline characteristics to be summarized

See Draft Table 1 below.

Details of how baseline characteristics will be descriptively summarized

Baseline characteristics will be descriptively summarized as show in Draft Table 1.S

Draft Table 1. Baseline Sample Characteristics

Sample Characteristics	Condition 1 (n=XXX)		Condition 2 (n=XXX)		Condition 3 (n=XXX)		Total Sample (n=XXX)	
	% or mean	95% CI	% or mean	95% CI	% or mean	95% CI	% or mean	95% CI
Gender								
Male								
Female								
Age, years								
Race								
White								
Black or African American								
Other Race								
Ethnicity								
Latino/Hispanic								
Non-Latino/Hispanic								
Education								
<High School (HS)								
G12 or GED, HS Diploma								
Some College								

Associate's degree								
Bachelor's degree								
Graduate or professional degree								
Poverty Status								
Below Poverty Line								
Above Poverty Line								
Sexual Orientation								
Straight or heterosexual								

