Gay, lesbian, or bisexual								
Current Cigarette Smoking								
Current smoker								
Nonsmoker								
Fagerstrom Nicotine Dependence Score (FTND)								
Trust in FDA								
Number of Times Participants Viewed a Message During Follow Up								

To update Table 1 see 'Table 1 V1.xlsx' in Analysis Plan folder

Analysis

Outcome definitions

- Quit intentions [Time Frame: day 16] PRIMARY OUTCOME
 - 3 item measure with high reliability, average of the 3 items to create a score range 1-4 (Brewer et al., 2016, 2018; Klein, Zajac, & Monin, 2009)
 - We will compare the differences between pre and post
- Number of cigarettes smoked each day [Time Frame: Measured daily on days 1-15]
 - Continuous, Modified from FTND (Heatherton, Kozlowski, Frecker, & Fagerström, 1991; Storr, Reboussin, & Anthony, 2005)
- Number of cigarettes forgone each day [Time Frame: Measured daily on days 1-15]
 - Continuous, adapted from Brewer 2016 (Brewer et al., 2016)
 - May be zero inflated, if yes, may choose to dichotomize to 0/1
- Number of cigarettes butted out each day [Time Frame: Measured daily on days 1-15]
 - Continuous, adapted from Brewer 2016 (Brewer et al., 2016)
 - May be zero inflated, if yes, may choose to dichotomize to 0/1
- Quit attempts during the study [Time Frame: Measured on days 16 and 32]
 - Adaptation from Fagan (Fagan et al., 2007)
 - May be zero inflated, if yes, may choose to dichotomize to 0/1
- Awareness of quitline [Time Frame: Measured on day 16]
- Recall of quitline phone number [Time Frame: Measured on day 16]
- Use of the quitline during the study [Time Frame: Measured on days 16 and 32]
- Intention to use the quitline [Time Frame: Measured on days 16 and 32]
- Quit intentions [Time Frame: Measured on day 32]
 - 3 item measure with high reliability, average of the 3 items to create a score range 1-4 (Brewer et al., 2016, 2018; Klein et al., 2009)
 - We will compare the differences between pre and post
- Self Efficacy [Time Frame: Measured on days 16 and 32]

- 1 item (“IARC HANDBOOKS OF CANCER PREVENTION,” n.d.; Thrasher, Swayampakala, Borland, et al., 2016; Thrasher, Swayampakala, Cummings, et al., 2016)
- Response Efficacy [Time Frame: Measured on days 16 and 32]
 - 1 item (Thrasher, Swayampakala, Cummings, et al., 2016)

Analysis Methods

Analysis methods will depend on the time point that the outcome was measured. Post test measures will be analyzed differently than measures from the daily surveys, as outlined below.

Post test measures

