What analysis method will be used and how treatment effects will be presented

Linear regression for continuous outcomes, logistic for dichotomous.

Any adjustment for covariates

Covariates included for the imputation (in addition to treatment group):

- Dose of ads (# of times participants viewed a message)
- Gender (Male, Female, Other) (The GenIUSS Group, 2014)
- Age (continuous)
- Poverty Status (Above or Below Poverty Line)(Brewer et al., 2018; Department of Health and Human Services, 2017)
- Education (6 categories, same as phone survey)
- FTND Sum Using scoring from Heatherton et al. 1991 (Fagerstrom Test for Nicotine Dependence)(Fagerstrom, Heatherton, & Kozlowski, 1990; Heatherton et al., 1991)

Covariates included in the analysis model (in addition to treatment group):

- Dose of ads (# of times participants viewed a message)

Methods used for assumptions to be checked for statistical methods

For continuous outcomes, we assume the distribution of dependent variable given a predictor variable (intervention) is 1) independent 2) normality 3) constant variance (homogeneity of variance). We can check normality with Q-Q plot of the residual or perform Wilk-Shapiro test and use a scatter plot of residual on predictor variable (intervention) to check independence and constant variance.

Details of alternative methods to be used if distributional assumptions do not hold (eg normality, proportional hazards, etc)

If we have a violation for normality assumption, we can have two options: 1) transform our data so that the shape of our response variable become normally distributed or 2) choose the non-parametric method like Kruskal-Wallis which does not require the assumption of normality. The ANOVA can be considered a robust test against the normality assumption though. If the assumption of homogeneity of variances has been violated, we can use Welch or Brown and Forsythe test. Even though we alternatively perform a Kruskal-Wallis test, in most cases, Welch test is best. We don't expect to have dependency issues in our data.

Any planned sensitivity analyses for each outcome where applicable

Sensitivity analyses may be carried out using a 'complete case analysis' framework

Any planned subgroup analyses for each outcome including how subgroups are defined

None a priori

Missing Data

Multiple imputation will be used so that everyone who was randomized to an intervention will be included in the primary analysis

Additional Analyses

None a priori

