Daily Questionnaire Measures

What analysis method will be used and how treatment effects will be presented

Mixed models to account for repeated measures of the same participant.

Any adjustment for covariates

Covariates included in the analysis model (in addition to treatment group):

- Dose of ads (# of times participants viewed a message)

Methods used for assumptions to be checked for statistical methods

Linear mixed model is an extremely flexible for modeling continuous outcomes. It turns out that linear mixed models are robust to violations of some of their assumptions. The followings are the assumptions for linear mixed model: 1) Independent (The outcomes of different people are assumed to be statistically independent of each other.) Note: the outcomes within a person are correlated. 2) Normality (random effects are assumed to be normally distributed with mean zero and the residuals are normally distributed.)

Details of alternative methods to be used if distributional assumptions do not hold (eg normality, proportional hazards, etc)

Because mixed models are robust to violations of some of their assumptions, we do not anticipate needing to use an alternative method.

Any planned sensitivity analyses for each outcome where applicable

None a priori

Any planned subgroup analyses for each outcome including how subgroups are defined

None a priori

Missing Data

Mixed models are appropriate to use and robust to missing data, so we will be able to include everyone who completed at least 1 daily questionnaire.

Additional Analyses

None a priori

Harms

Adverse events were not expected in this trial due to the minimal risks to participants, and no threat to participant health, so this section is not applicable.

Statistical Software

Statistical analyses will be conducted in SAS 9.4 (Cary, NC)

References

Final Dataset: rct_combined_07232018 [location removed]

Data Cleaning Syntax: 01_Create_Analytic_Files.sas [location removed]

Study Protocol: RCT_Protocol_V5 [location removed]

[figure not shown]
Analysis plan compiled according to “Guidelines for the Content of Statistical Analysis Plans in Clinical Trials” (Gamble et al., 2017)

- Brewer, N. T., Hall, M. G., Noar, S. M., Parada, H., Stein-Seroussi, A., Bach, L. E., ... Ribisl, K. M. (2016). Effect of Pictorial Cigarette Pack Warnings on Changes in Smoking Behavior: A Randomized Clinical Trial. *JAMA Internal Medicine*, *176*(7), 905–912. <https://doi.org/10.1001/jamainternmed.2016.2621>

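### The only sensitivity analysis for day-16 quit intention is an optional complete-case run, which cannot test loss that depends on the unseen score or on variables left out of the imputation

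*Combined protocol and SAP*

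**What the plan says.** The SAP section on outcome definitions names the primary outcome as "Quit intentions [Time Frame: day 16] PRIMARY OUTCOME", the mean of three items on a 1-4 scale, and adds "We will compare the differences between pre and post". It does not say whether the modelled variable is a change score or the post-test score.

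Under Post test measures, the missing-data entry reads "Multiple imputation will be used so that everyone who was randomized to an intervention will be included in the primary analysis". The imputation variables listed are treatment group, dose of ads (messages viewed), gender, age, poverty status, education and FTND. Baseline quit intention is collected at pre-test but is not on the list; nor are the daily answers on thinking about quitting. The analysis model contains treatment group and dose only.

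The sensitivity entry for these outcomes is "Sensitivity analyses may be carried out using a 'complete case analysis' framework". The verb is permissive, and no additional analyses are planned. No analysis that departs from missing at random appears anywhere in the document.

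Two descriptive items bear on loss. Post-test completion is reported as a percentage by arm (Adherence and Protocol Deviations). Under Withdrawal/follow-up, the timing of withdrawal is tabulated by arm, and "Numbers (with reasons) of loss to follow up and withdrawal over the course of the trial will be summarized by treatment group".

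For the daily outcomes, the SAP plans no sensitivity analysis and states "Mixed models are appropriate to use and robust to missing data".

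**The concern.** A sensitivity analysis for missing data is useful when it relaxes the assumption on which the main analysis depends. Here the main assumption is that a non-responder has the same expected day-16 score as a responder with the same arm, dose and five baseline characteristics. Complete case does not relax that assumption. It makes a similar one with fewer conditioning variables.

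The design gives the question some force. Messages and outcomes come through the same surveys, so a smoker who stops tolerating the messages also drops out of the outcome data. The arms differ in content, so the reasons for stopping may differ by arm. Reactance to the messages is asked only at post-test 1, and is therefore unknown for those who do not answer it.

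If people with low intention to quit leave one arm more than another, the imputed and complete-case contrasts would both be shifted in the same direction. Their agreement would say little about whether the loss mattered.

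**Working it through.** **Inputs.** From the documents: d = 0.25 for optimal versus sub-optimal, 80% power, alpha 0.05, 253 per group, a target of 800 allocated equally (about 267 per arm), and the two variable lists above. Assumed, because the documents give no figure: the loss rate, the strength of selection, whether selection acts in one arm or all, and the variance explained by covariates. Scores are in SD units.

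**1. The plan's own figure.** n per group = 2(1.96 + 0.8416)²/0.25² = 251.2, so 252. The t-test solution is 252.13, so 253. The stated 253 is reproduced with a two-sided alpha.

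**2. The two assumptions side by side.**
- Complete case: loss is ignorable given arm and dose.
- Imputation: loss is ignorable given arm, dose, gender, age, poverty status, education and FTND.

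The only systematic difference is the five baseline characteristics. The comparison can detect loss that works through them, and nothing beyond them.

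**3. Simulation with the two variable lists.** 1,500 trials per scenario, 267 per arm, about 20% missing. The model includes dose (unrelated to the score here), five covariates explaining about 11% of variance, and baseline quit intention assumed to explain 36%.

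| Loss mechanism | True d | Complete case | Planned imputation | Imputation plus baseline intention |
|---|---|---|---|---|
| One arm, listed covariates | 0 | 0.058 | -0.002 | -0.002 |
| One arm, baseline intention | 0 | 0.106 | 0.107 | -0.001 |
| One arm, unseen score (slope -1.0) | 0 | 0.177 | 0.159 | 0.096 |
| One arm, unseen score (slope -1.0) | 0.25 | 0.425 | 0.405 | 0.342 |
| Both arms alike, unseen score | 0.25 | 0.249 | 0.249 | 0.249 |

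The average within-trial gap between complete case and planned imputation is 0.060 in the first row, so that mechanism shows up. With one-arm loss on the unseen score it is 0.022, against 0.016 when data are missing completely at random, so that mechanism barely shows. Adding baseline intention removes the bias in the second row. In the fourth it reduces the bias from 0.405 - 0.25 = 0.155 to 0.342 - 0.25 = 0.092.

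**4. Varying the loss rate.** True d = 0.25, one-arm loss on the unseen score with logit slope -0.8 per SD, imputation from arm and weakly predictive demographics, no dose term.

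| Missing | Complete case | Imputation |
|---|---|---|
| 10% | 0.327 | 0.324 |
| 20% | 0.395 | 0.389 |
| 30% | 0.455 | 0.447 |

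The mean gap within a trial is 0.007 to 0.016. The imputation estimates are too large by 0.074/0.25 = 30%, 0.139/0.25 = 56% and 0.197/0.25 = 79%. Three changes shrink the bias:
- Adding the dose term, with an assumed correlation of 0.4 with the score, lowers the 20% row to 0.366 and 0.361.
- Slopes of -0.2 and -0.4 at 10% missing give 0.267 and 0.285.
- The same selection in both arms gives 0.245 to 0.254.

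**5. Tipping point.** If missing scores in one arm lie delta SD below their imputed values, the contrast falls by m × delta, where m is the missing share. With shifts in two arms the change is the difference of the two products. For an observed d = 0.25, using the completers' standard error SE = √(2/(267(1 - m))), significance is lost at delta = (0.25 - 1.96 × SE)/m.

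| m | SE | 0.25 - 1.96 × SE | delta |
|---|---|---|---|
| 5% | 0.0888 | 0.0760 | 1.52 SD |
| 10% | 0.0912 | 0.0712 | 0.71 SD |
| 20% | 0.0968 | 0.0603 | 0.30 SD |
| 30% | 0.1034 | 0.0472 | 0.16 SD |

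**The case against.** The strongest reply is that harm to the contrast needs selection that differs by arm. The two constituent-message arms share their text and images and differ only in the FDA source and quit information. Similar selection in both is plausible, and the powered contrast is then nearly unbiased. This stands: unequal selection is an assumption, and the documents neither support it nor rule it out. It is less reassuring for the comparison with the littering messages, where content differs more.

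The plan also tabulates completion, timing and reasons for loss by arm, which could reveal unequal loss. That stands too, but such tables do not turn unequal loss into an effect on the estimate. Equal percentages can also hide unequal selection: in the one-arm scenario of step 3, loss was 21% and 20%.

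Conditioning on dose helps if disengaged smokers view fewer messages. It reduced the bias in step 4 but did not remove it. If the change score itself is imputed and analysed, baseline intention enters through the outcome, so the size of the second row in step 3 may differ. The SAP leaves this open.

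A reader might infer that the complete-case comparison can reveal no selective loss at all. It can: loss driven by the listed characteristics separates the two analyses. A reader might also infer that the SAP treats agreement between them as proof that loss was harmless. It makes no such statement.

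**Conclusion.** The gap is real. The one check named for the primary outcome is optional, and it cannot test loss that depends on the unobserved day-16 score or on variables outside the imputation model. That conclusion follows from the two variable lists and needs no assumed rate.

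The size is conditional. Estimates of about 0.33, 0.39 and 0.45 for a true 0.25 require one-arm selection, a slope of -0.8 per SD and 10 to 30% loss, all assumed. It would be wrong to read these as a forecast that the trial's effect will be overstated, because weaker or equal selection gives much less bias or none. The tipping points rest on fewer assumptions: a loss rate, an observed d of 0.25 and the completers' standard error. At 5% loss the result is hard to overturn (about 1.5 SD). At 20 or 30% a modest shift is enough (0.30 or 0.16 SD).

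This is an inexpensive improvement that should be made, not a flaw that invalidates the primary analysis. The wording on mixed models is a side point about non-primary outcomes.

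**What to change.** - Add baseline quit intention, already collected at pre-test, to the imputation model.
- Make mandatory a delta-adjusted analysis built on those imputations, with shifts set by arm and including the case where only one constituent-message arm is shifted.
- Express the shift in units of the observed SD, since the documents give none for this score. Widen it until each primary contrast loses significance or imputed values reach the limit of the 1-4 scale. A short fixed range would not do: a grid ending at 0.75 SD would miss the crossing at 5% loss.
- Report the tipping point for each primary contrast beside the attrition tables by arm that are already planned.
- Keep complete case as a descriptive result.
- In the daily-measures section, limit the missing-data statement to validity under missing at random.

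The cost is SAP wording and a short loop in the planned SAS 9.4 (the MNAR statement of PROC MI with its ADJUST option). No new data are needed. The downside is one extra table, which may make the conclusion look less firm.

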7. Have not participated in a smoking study, other than phone survey, in last 3 months
8. Able to complete a survey on a computer
9. Able to complete a survey in English
10. Able to complete surveys delivered via email
11. Able to complete 3, 20-minute, surveys
12. Able to complete a 5-min survey each morning for 15 days
13. Lives in the US

Experimental Conditions

- Optimal Group: receive the risk and constituent messages with optimized source depiction and engagement formats.
- Suboptimal Group: receive the risk and constituent messages without source or engagement text.
- Control Group: receive littering messages

Allocation and Blinding

Participants will not be informed specifically about the possible interventions that they may be assigned to. Researchers will not be blinded to the condition that participants had been assigned to, however all outcome measures will be assessed via online survey.

At the end of the baseline survey, survey software will randomly assign participants to one of the three study arms. Participants will have an equal chance of being randomized to each study arm.

Messages

Constituent Message	Words (Characters)	Littering Message	Words (Characters)

CIGARETTE SMOKE CONTAINS URANIUM THIS CAUSES LUNG TUMORS AND KIDNEY DAMAGE
 	11 (76)	
PLEASE REFRAIN FROM LITTERING CIGARETTE BUTTS ARE THE MOST LITTERED ITEM
 	11 (74)

CIGARETTE SMOKE CONTAINS ARSENIC THIS CAUSES HEART DAMAGE
 	8 (59)	
CIGARETTE BUTTS DON'T BIODEGRADE PLEASE DO NOT LITTER
 	8 (55)

CIGARETTE SMOKE CONTAINS FORMALDEHYDE THIS CAUSES THROAT CANCER
 	8 (65)	
CIGARETTE LITTER REQUIRES CLEANUP DISCARD CIGARETTE BUTTS PROPERLY
 	8 (68)

[figure not shown]

CIGARETTE SMOKE CONTAINS LEAD THIS CAUSES CANCER AND BRAIN DISORDERS
 	
10 (70)
	
CIGARETTE LITTER POLLUTES THE EARTH DISPOSE OF CIGARETTE BUTTS CORRECTLY
 	
10 (74)

CIGARETTE SMOKE CONTAINS AMMONIA THIS CAUSES BREATHING PROBLEMS
 	
8 (65)
	
CIGARETTE BUTTS ARE POLLUTION PLEASE REFRAIN FROM LITTERING
 	
8 (61)

Study Flow

Pilot: Assess whether we can proceed and launch the full study when they have completed post-test 1, allow pilot participants to complete the full study (through post-test 2).

Full Study: Baseline survey, then a survey every morning for 15 days assessing previous day behavior and delivering a message. Follow up with post surveys at day 16 and 32.

Process:

Days 1-15: Morning Surveys

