The power calculation above is for a smaller effect size than the Noar 2016 paper, $d=0.25$. If we enroll 253 per group, we will have 80% power to detect a small difference between the optimal and sub-optimal group.

For our purposes, that would mean enrolling a total of at least 759 people.

How does this compare to [name]'s simulations?

Based on [name]'s simulations, if we use 3 time points, and enroll around 750 people, we should be able to see an effect size of 0.35. This simulation is also very dependent on the assumptions that we started with.

Recommendation:

To be even more conservative, I would like to enroll at least 800 participants into our study to have enough power to see a $d=0.25$ difference between the optimal and sub-optimal groups.

Framework

Superiority – standard hypothesis testing framework

Statistical Interim Analyses and Stopping Guidance

NA, this study is no more than minimal risk to participants and does not pose a risk to their health, so we did not carry out any interim analyses or set guidelines for stopping the trial early.

Timing of Final Analysis

Final analysis will take place after all data collection for the RCT is complete.

Timing of Outcome Assessments

Time	Pre-Test	Morning	Post-Test 1	Post-Test 2

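### The daily mixed models have no study-day or treatment-by-day term, so an effect that builds with repeated messages is diluted to a flat average and, under drop-out, underestimated

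*Combined protocol and SAP*

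**What the plan says.** The protocol's Study Flow section describes "Baseline survey, then a survey every morning for 15 days assessing previous day behavior and delivering a message". The SAP's Outcome definitions list three daily behavioural outcomes. The first is "Number of cigarettes smoked each day [Time Frame: Measured daily on days 1-15"; cigarettes forgone and cigarettes butted out have the same time frame. None of them is primary; the primary outcome is quit intentions at day 16.

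Under Analysis Methods, Daily Questionnaire Measures, the method is "Mixed models to account for repeated measures of the same participant". Below the line "Covariates included in the analysis model (in addition to treatment group" there is one entry, dose of ads, described as the number of times a participant viewed a message. Study day, treatment-by-day, the random effects, the covariance structure and the daily treatment contrast are not given. No sensitivity or additional analyses are planned in advance. On missing data the section says "Mixed models are appropriate to use and robust to missing data, so we will be able to include everyone" with at least one daily questionnaire.

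The SAP does not say whether dose is a per-person total or a running count. Draft Table 1 shows it as a single follow-up total per participant, which suggests a total but does not prove it.

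**The concern.** Each morning survey asks about the previous day and then shows that day's message. For someone who completes every survey, report 1 follows no messages and report 15 follows 14. One arm coefficient over all 15 reports cannot show whether an effect grows or fades as messages are repeated.

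Drop-out adds a second problem. Likelihood-based mixed models handle ignorable missing data properly only when the mean model is right. If the arm difference changes with day and the model has no such term, participants who leave early contribute only the days on which the effect is small, and the estimate falls below the true 15-day average. These three outcomes are the trial's daily measures of smoking behaviour.

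**Working it through.** **The plan's own figure.** The only sizing figure is for the primary outcome: "If we enroll 253 per group, we will have 80% power to detect a small difference between the optimal and sub-optimal group". At d = 0.25, two-sided alpha 0.05 (sidedness assumed), the normal approximation is 2 × (1.960 + 0.842)² / 0.25² = 251.2, so 252 per arm. The exact t calculation gives 253 (power 0.8014). The figure is reproduced, but it concerns quit intention measured once. The documents size nothing for the daily models.

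**Assumed inputs, none from the documents.** Between-person SD 8 and within-person SD 3 cigarettes/day; an effect growing linearly from 0 at report 1 to 1 cigarette/day at report 15. From the plan: 15 reports, and 800 / 3 ≈ 267 per arm.

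**Step 1: dilution with complete data.** The flat term estimates the mean of (day - 1)/14 over days 1 to 15, which is 0.50 cigarettes/day.

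**Step 2: dilution with drop-out.** Expected-value generalised least squares with a random intercept, 30% monotone drop-out in both arms, spread evenly over days (true 15-day average -0.50):

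| Fixed effects | Arm estimate |
|---|---|
| Arm only | -0.42 |
| Arm + total dose (as planned) | -0.42 |
| Arm + dose + categorical day | -0.42 |
| Arm + dose + day + arm-by-day (day centred) | -0.50 |

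The shortfall is (0.500 - 0.422) / 0.500 = 16%. Dose does not repair it and neither does a day main effect; the arm-by-day term does.

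**Step 3: power, complete data, 267 per arm.**

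- Flat term, without a random slope: SE = sqrt(2 × (64 + 9/15) / 267) = 0.696; z = 0.50 / 0.696 = 0.72; power 11%.
- Growth over the 14 day-steps, with random-slope SD s per day: SE = 14 × sqrt(2 × (s² + 9/280) / 267), where 280 is the sum of squared deviations of days 1 to 15 from their mean.

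| s per day | SE | Power for growth of 1 |
|---|---|---|
| 0.1 | 0.249 | 98% |
| 0.2 | 0.325 | 87% |
| 0.3 | 0.423 | 66% |
| 0.5 | 0.644 | 34% |

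**Step 4: does a common trend leak into the arm effect?** Here the true arm effect is zero and smoking declines linearly in every arm.

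- Equal drop-out (20% in each arm): bias 0.000, with or without day.
- Unequal monotone drop-out: a 2-cigarette decline with 40% against 20% shifts the estimate by 0.105 cigarettes/day if dose is left out; a 3-cigarette decline with 50% against 20% shifts it by 0.236. With dose included, as planned, both shifts are 0.000, whether dose is a total or a running count. For a total, the reason is that a participant's mean observed day is (dose + 1)/2, so dose absorbs a linear trend.
- Non-linear common trends of about 1 SD, total dose included: residual bias at most about 0.007 SD.
- Unequal intermittent missingness rising with day (to 40% against 20%, or 50% against 10%), common trend of 1 SD: at most about 0.002 SD with total dose, 0.03 to 0.06 SD with a running count, and 0.000 once day is added.

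**The case against.** The 15-day average is a legitimate effect measure, and the fix keeps an average as the main contrast. That contrast gains almost no power. Over reports 2 to 15 the assumed effect averages 7.5/14 = 0.536, with SE sqrt(2 × (64 + 9/14) / 267) = 0.696, so power is about 12%. The high figures belong only to an added secondary contrast. They depend on an assumed slope SD and on a linear effect, the shape that favours a slope test. If the effect is immediate and constant, the growth contrast gains nothing. The SAP's objectives concern quit intention and do not hypothesise growth in the daily outcomes. The section also leaves out random effects and covariance, so the missing day term may be incomplete specification and not a decision. The extra contrast enters a plan with no multiplicity adjustment.

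All of this stands as a limit on the point. It does not remove the underestimation in step 2, which affects the average itself. Incomplete wording would also leave day, interaction and contrast to be chosen after the data are seen.

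A reader might infer that late drop-out or a shared decline in smoking is reported as an arm effect. The documents do not support that for the planned model. Equal missingness gives no bias, and the planned dose term removes the leakage from unequal monotone drop-out under a linear trend. Nor is a building effect lost altogether: it is reduced to its average.

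**Conclusion.** The point holds for the three secondary daily outcomes. As written, the model gives one flat difference. For a building effect, this halves the final-day value when data are complete (0.50 against 1) and, under the assumed 30% drop-out, falls about a further 16% below the true average despite the dose term. The SAP's claim of robustness to missing data is therefore too broad. The sizes rest on assumed variances, effect shape and drop-out, and on missingness unrelated to outcome.

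Leakage of a common trend is conditional. It becomes material only if dose, itself measured after randomisation, is removed from the model, or if dose is a running count and intermittent missingness differs between arms. Protection against it should not rest on an undefined post-randomisation covariate. This is a cheap improvement to the secondary analyses and leaves the primary analysis and the sample size as they are.

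**What to change.** In the SAP, Daily Questionnaire Measures:

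- Add study day (categorical, or linear with a random slope) and treatment-by-day to the fixed effects of each daily model. A day main effect alone is not enough.
- State the main contrast as the arm difference averaged with equal weight over the post-message days, that is reports 2 to 15, since report 1 precedes any message.
- Pre-specify one secondary contrast: arm-by-day growth, or the final-week arm difference.
- Define dose as a total or a running count, and name the covariance structure.
- Replace the robustness statement with one that makes validity depend on ignorable missingness and a correctly specified mean model.

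The cost is SAP wording and a few lines of SAS, with no new data. The downside is one extra unadjusted secondary contrast per daily outcome, which is uninformative if the effect is immediate and constant.
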